8	Visit 9, Week 29 (-5/+5 day window)
9	Continuing treatment with 25% inhaled corticosteroid dose and Vitamin D/placebo.
10	Procedures Performed:
11	Asthma Control Test
12	Asthma Symptom Utility Index
13	Review of Participant Adherence with Study Medications
14	Diary, Cold Questionnaire and Peak Flow Review
15	Spirometry
16	Treatment Failure Assessment
17	Dispensation of Randomized Study Drugs
18	Visit 10, Week 33 (-5/+5 day window)
19	This visit will conclude the study.

1	End treatment with 25% innaled corticosteroid dose and Vitamin D/placebo.
2	Procedures Performed:
3	Height, weight; waist, hip, neck (anthropometrics)
4	Physical examination (long)
5	Asthma Control Test
6	Asthma Symptom Utility Index
7	Asthma-specific Work Productivity and Activities Impairment Questionnaire
8	Asthma Bother Profile
9	Perceived Stress Scale
10	Review of Participant Adherence with Study Medication
11	Diary, Cold Questionnaire and Peak Flow Review
12	Urine Pregnancy Test (for all women of child-bearing potential)
13	Spirometry
14	Treatment Failure Assessment
15	Serum 25 (OH) D Measurement
16	Urine calcium/creatinine ratio measurement
17	Vitamin D Dietary Intake Questionnaire
18	Sun Exposure Questionnaire

1	Skin Pigmentation (Melanin) Measurement
2	AsthmaNet Satisfaction Questionnaire
3	Exit Interview
4	Exit visit (in those participants who have been randomized and are withdrawing consent or meet drop-
5	out criteria (i.e., more than two treatment failures))
6	Asthma Control Test
7	Review of Participant Adherence with Study Medication
8	Diary, Cold Questionnaire and Peak Flow Review
9	Spirometry
10	Treatment Failure Assessment
11	Serum 25 (OH) D Measurement
12	Exit Interview
13	Treatment failure or Exacerbation Visit
14	This visit will be performed if a participant experiences treatment failure or exacerbation conditions
15	between regularly-scheduled study visits and needs to be seen at the clinical site. Procedures to be
16	performed include:
17	Physical Examination (long)
18	Asthma Control Test
19	Review of Participant Adherence with Study Medication

- Diary, Cold Questionnaire and Peak Flow Review
- 2 Spirometry
- 3 Treatment Failure Assessment

D. Study Procedures

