be applied with the Multi-Test II device using standard preparations from Greer Laboratories (Lenoir, NC). After 20 minutes, the outer contour of the wheal reaction is outlined using a fine felt-tip pen, and the result is expressed as the mean of the lengths of the longest diameter and the perpendicular line through its center. A skin prick test is considered positive if the mean length at 20 minutes after the skin prick is at least 2 mm larger than the size of the negative control. Medications need to be held prior to the allergy skin test include: first generation antihistamines (3 days), second-generation antihistamines (7 days), topical nasal antihistamines (5 days), non-SSRI antidepressants (3 days), and H₂ blockers (3 days) as per AsthmaNet MOP.

Asthma symptoms and control. Asthma symptoms will be assessed by diary recall of asthmacontrol days (ACD) and rescue-free days (RFD), at all visits and by using a standardized questionnaire (ASUI) in all participants at Visits 1, 3 and 5-10. ACD are days recorded in daily diary without any asthma symptoms or rescue levalbuterol use. RFD are days recorded in daily diary without levalbuterol use. The Asthma Symptom Utility Index (ASUI) provides a validated quantitative assessment of asthma symptoms during the prior two weeks (82). Asthma control will be assessed by the Asthma Control Test (ACT) (83) in all participants at Visits 1, 3, 5-10 and at additional treatment failure visits scheduled between regular clinic visits.

Asthma-specific quality of life questionnaires (QOL). QOL will be measured in all participants at Visits 1, 3 and 10 using an asthma-specific instrument, the Asthma Bother Profile (ABP). The Asthma Bother Profile is a 22 item measure designed to assess adult patient perception of the asthma experience and distress, as well as patient perception of their asthma management. This asthma quality of life measure is unique among currently available measures in its emphasis on the psychosocial impact of asthma, including items measuring perceived bother, mood, fear, social relations and financial impact.

Sinonasal Questionnaire (SNQ). Sinusitis and rhinitis are very common in asthma and may lead to poorly controlled asthma. We will explore the effect of vitamin D on sinusitis and rhinitis using the

- sinonasal questionnaire (SNQ) at visits 3 and 6. The SNQ is a sensitive, specific and reproducible
- 2 instrument to screen for sinonasal disease (88).

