- 3 Vitamin D Intake Questionnaire. Participant dietary intake of vitamin D (and other vitamin
- 4 supplements) will be assessed at visits 3 and 10 using a modified food frequency questionnaire (95).
- 5 Assessment of the responses to these questionnaires will help account for dietary sources of vitamin
- 6 D in addition to the study intervention.
- 7 Sun Exposure Questionnaire (SEQ). We will collect UV exposure history using a modification of
- the UV exposure questionnaire that is used in the Nurses' Health Study (Appendix C) (96) at visits 3
- 9 and 10. Briefly, this questionnaire will inquire about UV exposure information such as average hours
- per dayspent outdoors in summer and winter, and sunscreen and tanning salon habits.
- 11 Asthma-specific Impairment. Impairment from asthma, in terms of productivity loss and activity
- impairment, will be assessed using an asthma-specific version of the Work Productivity and Activity
- 13 Impairment questionnaire (WPAI:Asthma) in all participants. The WPAI:Asthma has been previously
- validated in a severe difficult-to-treat asthma population in The Epidemiology and Natural History of
- 15 Asthma: Outcomes and Treatment Regimens (TENOR) study (85). WPAI:Asthma questionnaire will
- be measured at visits 2 and 10.

24

- 17 Cold Questionnaire. In all individuals experiencing a cold during the trial, the potential impact of
- vitamin D on respiratory tract infections will be evaluated. The frequency and severity of self-reported
- 19 colds, as reflected by the peak Wisconsin Upper Respiratory Symptom Survey-21 (WURSS-21) score
- 20 (86) during the cold, will be compared between those in the vitamin D treatment group to those
- 21 receiving placebo. Instructions on how to complete the WURSS-21 at the onset of cold symptoms will
- 22 be reviewed at visit 4 and reinforced at each subsequent visit. Secondary analysis of the severity of
- the cold will evaluate the effect of the intervention on day 1 and 2 WURSS-21 scores.
 - Stress Questionnaire (PSS). Psychological stress is a well known co-morbidity in asthma that

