occurs as a result of having chronic respiratory symptoms that limit activity and reduce quality of life (97-99). Moreover, psychological stress is also a risk factor for asthma associated with lower FEV₁, reduced asthma control and asthma-related quality of life, increased exhaled nitric oxide levels and higher serum IgE levels (100-102). These psychological stress-related associations may be mediated via mechanisms involving up-regulation of inflammatory cytokines and increased cortisol production via activation of the hypothalamic-pituitary axis, which can lead to corticosteroid resistance. This has been shown in vitro by the reduced capacity of corticosteroid to suppress interleukin-6 production (103, 104). Levels of perceived stress will be assessed at visits 2 and 10 using an adapted version of the Perceived Stress Scale (PSS) (87). This is a short 10-question instrument that has been validated in adults.

Skin Pigmentation (Melanin). Participants will have the degree of pigmentation/melanin measured at visits 3 and 10 using the Smart Probe 400 (IMS, Inc, Milford, CT). This is a spectrophotometer device that measures degrees of pigmentation on a continuous scale from 0 to 100, 0 being absolute black and 100 being absolute white. Each participant will have pigmentation measurements recorded from the exposed forearm, upper inner arm, forehead and abdomen, with two readings averaged and recorded at each location (Appendix D).

 U_{Ca}/U_{Creat} ratios. Urinary calcium to creatinine (U_{Ca}/U_{Creat}) ratios will be measured at visits 1, 3, 5, 6, 8 and 10. While others have found the dose of 4,000 IU/day vitamin D to be safe and effective at raising 25(OH)D levels, we will monitor U_{Ca}/U_{Creat} ratios as this is the earliest abnormality detected and most non-invasive way of monitoring for hypervitaminosis D (91). If a U_{Ca}/U_{Creat} is greater than 0.37 (urinary Ca and Creat in mg), the participant will be instructed to increase hydration and a repeat measurement will be obtained 30 days later. If the repeat U_{Ca}/U_{Creat} is elevated, then the participant will be instructed to hold study drug and have a serum calcium and 25(OH)D level obtained. If either the calcium or 25(OH)D is elevated, the participant will stop study drug. If the calcium and 25(OH)D are normal, then the participant may resume study drug.

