The recommended dose of prednisone used during an acute exacerbation shall consist of 60 mg as a single dose every day for 3 days, followed by a 10 mg/day taper over the next 5 days. The decision to initiate or to continue a course of prednisone beyond 8 days is left to the discretion of the physician.

E. Study Center Visits Following Treatment Failures or Exacerbations

For safety reasons, all participants will be seen within one week from the date of the treatment failure or exacerbation. Trial drugs will be continued during a treatment failure or an exacerbation unless the treating physician considers it appropriate to suspend such therapy until the event resolves. Following this "safety" visit, subsequent protocol visits will continue in accordance with the visit schedule established at trial entry.

F. Criteria for Achieving Dropout Status

Participants may be assigned "drop-out" status during the double-blind treatment period if they become pregnant or if they withdraw consent. In addition to the usual reasons for withdrawing consent (moving to another region, inconvenience, etc.), it will be noted if a participant withdraws consent due to lack of satisfaction with the quality of asthma control. At this visit, study termination procedures will be conducted, all study medications stopped, and the participant will begin a treatment plan at the direction of the examining physician.

G. Criteria for Withdrawal from Study Based on Treatment Failures or Asthma Exacerbations

Participants experiencing any treatment failure during the run-in or OCS response period will be terminated from study participation and allowed to re-screen one additional time after a period of 2 or more weeks following resolution of the event.

Once randomization has occurred at visit 4, intention-to-treat principles will apply. As treatment failure is the primary outcome, and since treatment failure criteria are consistent with a less severe worsening of asthma than experienced during an exacerbation, participants will not be terminated from study participation until more than two treatment failures or exacerbations have occurred. Once achieving the third treatment failure or exacerbation event, the participant will be withdrawn from the blinded phase of the trial and will be seen in the AsthmaNet clinic for a final study exit visit.

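### The early Exit visit omits the three questionnaires (ABP, WPAI:Asthma, PSS) whose only post-randomisation measurement is Visit 10, so early leavers have baseline values only for these secondary outcomes

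*Protocol*

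**What the plan says.** Protocol section VI.C describes an "Exit visit (in those participants who have been randomized and are withdrawing consent or meet drop"-"out criteria (i.e., more than two treatment failures"). Its procedures are the Asthma Control Test (ACT), adherence review, review of diary, cold questionnaire and peak flow, spirometry, treatment failure assessment, serum 25(OH)D and an exit interview.

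Section VI.D fixes when the three questionnaires are given:

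- ABP: "QOL will be measured in all participants at Visits 1, 3 and 10 using an asthma-specific instrument".
- WPAI:Asthma: to "be measured at visits 2 and 10".
- PSS: "Levels of perceived stress will be assessed at visits 2 and 10".

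Section X.G states that intention-to-treat principles apply from Visit 4 onward, and also that "Once achieving the third treatment failure or exacerbation event, the participant will be withdrawn from the blinded phase of the trial" and seen for a final exit visit. Section III.D lists quality of life, impairment and stress among the secondary outcome measures and baseline variables. Section VIII.C assumes data missing at random (MAR), with pattern-mixture modelling as the fallback.

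**The concern.** For most secondary outcomes, an early leaver has some post-randomisation values from intermediate visits. For these three there is one chance, Visit 10, and the visit that replaces it for early leavers does not take it up.

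One route to the Exit visit is a third treatment failure or exacerbation, so some of the missing values are missing because the asthma went badly. Section X.F foresees another related route: withdrawal of consent because of dissatisfaction with asthma control. If vitamin D prevents failures, placebo should lose more participants with poor scores, and a comparison of those who reach Visit 10 would understate the benefit on these outcomes. No later analysis plan can recover data that were never collected, so the visit list is the place to act.

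**Working it through.** **Schedules compared** (randomisation is at Visit 4). Sections VI.C, VI.D and Appendix E agree on the following.

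| Measure | Before randomisation | After randomisation | At Exit visit | At treatment failure visit |
|---|---|---|---|---|
| ABP | Visits 1, 3 | Visit 10 | no | no |
| WPAI:Asthma | Visit 2 | Visit 10 | no | no |
| PSS | Visit 2 | Visit 10 | no | no |
| ASUI | Visits 1, 3 | Visits 5–10 | no | no |
| Urine calcium/creatinine | Visits 1, 3 | Visits 5, 6, 8, 10 | no | no |

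A participant who leaves before Visit 10 has no post-randomisation ABP, WPAI:Asthma or PSS. Appendix E has no Exit column that might add them.

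**What the planned models can do.** With one post-baseline value per outcome, a repeated-measures model of that outcome has only the baseline to inform a leaver's missing value. A pattern-mixture model would have no observed post-randomisation value in the early-leaver pattern, so its result would rest wholly on the assumption put in.

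**Upper bound on numbers.** Section VIII.A gives 200 per group and 15% withdrawal: 0.15 × 400 = 60. This covers every reason for leaving.

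**Numbers leaving through repeated failure.** The protocol gives first-failure rates only: 40% in control and, at a hazard ratio of 1.8, 1 − 0.60^(1/1.8) = 24.7% on vitamin D. How often failures recur is an assumption. I took counts per participant as Poisson, or as negative binomial with frailty variance v, and chose the mean m to match the first-failure rate p: 1 − e^(−m) = p, or 1 − (1 + vm)^(−1/v) = p. For example, at v = 1 the probability of three or more is p³: 0.40³ = 0.064.

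If leavers score δ worse than completers, the completer mean is off by (proportion lost) × δ in each arm. The between-arm bias is then (difference in proportions lost) × δ. I took δ = 0.5 to 1 SD, also an assumption.

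| Recurrence assumed | P(≥3) control | P(≥3) vitamin D | Per 200, control vs vitamin D | Bias (SD) |
|---|---|---|---|---|
| Poisson | 0.0152 | 0.0031 | 3.0 vs 0.6 | 0.006–0.012 |
| v = 1 | 0.0640 | 0.0151 | 12.8 vs 3.0 | 0.024–0.049 |
| v = 2 | 0.1158 | 0.0311 | 23.2 vs 6.2 | 0.042–0.085 |
| v = 4 | 0.1984 | 0.0652 | 39.7 vs 13.0 | 0.067–0.133 |

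For scale, the difference detectable with 80% power at 170 per arm is (1.96 + 0.842) × √(2/170) = 0.304 SD. The last row is extreme: 39.7 + 13.0 = 52.7 third-event removals would use up nearly all of the 60 planned withdrawals.

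**The case against.** Nothing in the protocol says that the Exit visit must repeat Visit 10. It keeps ACT, spirometry, diary review and 25(OH)D, so the measures nearest the hypotheses are captured, and a shorter list spares a participant who is leaving. Quality of life, impairment and stress belong to none of the stated hypotheses. All of this stands. The omission is a design choice with a cost, not a contradiction, and the cost falls on lesser secondary outcomes.

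Third events may also be few. Section X.D expects most failures during the taper phases and stops further tapering after a second failure or an exacerbation, which leaves limited room for a third event before Visit 10. This too stands, and it favours the upper rows of the second table, though no figure in the protocol settles it.

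A score taken just after a third failure may reflect an acute state at an earlier week and on a different inhaled corticosteroid dose. It is not a Week 33 value, and pooling the two without distinction could bring in a bias of its own. This affects how the values are used, not whether to collect them.

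A reader might infer more than the documents support:

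- That some 60 participants are lost through repeated failure. The 15% also covers moving away, inconvenience and pregnancy.
- That these participants contribute nothing to the three outcomes. Their baseline values exist, and someone whose third event falls at Visit 10 could still be measured.
- That recovering everyone would cut the standard error by about 8% (√(400/340) = 1.085). That requires every leaver to attend and complete the forms, and exit scores to stand in for Week 33 scores.
- That ASUI and urine calcium/creatinine share the problem. Both are measured at other post-randomisation visits.

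**Conclusion.** The gap is real and follows from the schedule alone: a participant who leaves before Visit 10 has no post-randomisation ABP, WPAI:Asthma or PSS value, even if the Exit visit is attended. Part of the loss depends on outcome, because a third failure or exacerbation leads to that visit by rule.

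The size is uncertain. At most about 60 of 400 are affected, if all planned withdrawal precedes Visit 10; repeated failure may account for only a few per arm. Under Poisson recurrence or frailty variance 1, the bias through that route is at most 0.049 SD, about 16% of the 0.304 SD detectable difference. Larger values need strong clustering of failures. These figures assume the design effect on first failures and leavers 0.5 to 1 SD worse; with equal loss in both arms and the same δ, the bias is zero. If placebo loses more, the error is towards understating a benefit, so it would not create a false positive. The primary time-to-failure analysis is unaffected. This is a cheap improvement to secondary data, not a threat to the trial's main conclusion.

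**What to change.** In section VI.C, add ABP, WPAI:Asthma and PSS to the Exit visit procedures, and give the Exit visit its own column in Appendix E. Record the scores with their actual date as end-of-participation values, kept distinct from Week 33 values, and state whether they enter the secondary analyses directly or a sensitivity analysis. The withdrawal rule need not change.

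The cost is a short amendment and a slightly longer visit: the ABP has 22 items, the PSS 10 questions, and all three forms are already in use. Some participants will decline, particularly those withdrawing consent, and some exit scores will reflect a recent acute event, which is the reason for keeping them identifiable. Adding ASUI and urine calcium/creatinine at exit is optional, and the sole-measurement argument does not support it.

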Measurement of serum 25(OH) vitamin D - Liaison assay and quality control and blinding considerations. Participants will have peripheral blood collected for vitamin D level at visits 0, 6, 8 and 10. The DiaSorin LIAISON® 250H vitamin D assay is a fully automated system utilizing a direct competitive chemiluminescence immunoassay for the quantitative determination of 25OH vitamin D in serum or plasma. This method has equal specificity to both D2 and D3 forms and provides a total vitamin D result. The DiaSorin LIAISON® 250H vitamin D method is the only fully automated FDA cleared method available today. This assay maintains both inter and intra precision of less than 8% across the linear range. Linearity and recovery, which demonstrate an assay's accuracy, are both excellent with a mean recovery of 102% and an R-squared value for linearity of 0.99. The assay has a measuring range of 4.0 to 150 ng/mL. The results will be expressed in terms of 25-(OH)D and vitamin D insufficiency is defined as level <30 ng/ml. Toxic levels will be considered ≥120 ng/ml (105). Participants above this level will stop blinded study capsules and return to the clinical site for a repeat test as soon as possible. If the second vitamin D level is ≥120 ng/ml, the participant will stay off study capsules for the remainder of the study and will continue to be seen for follow-up visits (intention-totreat). If the repeat vitamin D level is normal, the participant will resume taking study capsules. The LIAISON® 25 OH Vitamin D TOTAL Control Set is used as assayed quality control samples to monitor the accuracy and precision of the DiaSorin LIAISON® 25 OH Vitamin D TOTAL Assay.

1

2

3

4

5

6

7

8

9

10

11

12

13

14

15

16

17

18

19

20

21

22

23

24

25

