In order to preserve the integrity of the blinding of the vitamin D/placebo study drug and to avoid the introduction of biases related to an assessment of the severity of a participant's baseline level of vitamin D insufficiency/deficiency, study participants, clinical personnel, and DCC staff who are directly involved in the day-to-day operations of the trial will not have access to the actual assay results from the screen visit or follow-up visits. The DCC will implement a reporting process such that site coordinators will be notified of the eligibility status of each screened participant (eligible or ineligible). If a follow-up vitamin D level (from visit 6, 8, or 10) is in the toxic range, an e-mail will be autogenerated through the AsthmaNet database and sent to the site coordinator and Principal

- 1 Investigator notifying them of the toxicity (but not giving them the specific assay results) so that
- 2 appropriate actions can be taken, as outlined above. This scenario is expected to occur rarely, if at
- 3 all, in this trial.

VII. DRUG SUPPLIES

A. Study drugs

The low dose inhaled corticosteroid will be ciclesonide (Alvesco®) 80 mcg/puff two puffs twice daily (total 4 puffs/day). The inhaled corticosteroid will be tapered to two puffs once daily in the AM in Phase IIa and one puff daily in the AM in Phase IIb (see VI.B). The rescue inhaled short-acting bronchodilator will be levalbuterol (Xopenex®). Ciclesonide and levalbuterol will be provided for the study by Sepracor, Inc.

Vitamin D_3 100,000 IU and 4,000 IU will be administered in capsules prepared by BIO-TECH Pharmacal, Inc. with matching placebo capsules. BIO-TECH Pharmacal, Inc. is one of 12 soft gelatin capsule manufacturers in the US and has provided study medication for other clinical trials. Because these doses of vitamin D_3 are not FDA approved for an asthma indication, an IND has been obtained from the FDA (#110227).

B. Rationale for Vitamin D₃ Dose and Treatment Duration

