Participants who experience two treatment failures during the run-in period or OCS response period (one each during two separate enrollments) will not be allowed to participate in the study further. This will enrich the study population for individuals who are likely to remain stable during the stable inhaled corticosteroid dose phase (Phase I) with the bulk of treatment failures likely to occur during the inhaled corticosteroid tapering phase (Phases IIa and IIb).

For participants who meet criteria for treatment failure during the post-randomization phases of the study, the dose of inhaled corticosteroid will be doubled and continued for 7 days. For treatment failures occurring during Phase I, the dose will be twice the inhaled corticosteroid stable dose. For treatment failures occurring during Phase II, the dose will be increased to the dose the participant was receiving prior to initiation of the most recent steroid taper (i.e. returned either to Phase I or Phase IIa dosing, as appropriate). If, after 7 days, the treatment failure episode is clinically-resolved, the corticosteroid stable dose (for treatment failures during Phase I) or pre-failure tapering dose (for treatment failures during Phase II) of inhaled corticosteroid will be resumed and study visits will continue as per protocol. If an exacerbation or second treatment failure occurs during the post-randomization phases of the study, no further inhaled corticosteroid dose tapering will be attempted.

For participants who experience a treatment failure event that also meets the criteria for a significant asthma exacerbation, dosing of inhaled corticosteroid depends on the phase in which the

event occurred. If the exacerbation occurs during Phase I, the dose of inhaled corticosteroid will be doubled (to 200% of the inhaled corticosteroid stable dose) for 7 days. If, after 7 days, the event is clinically-resolved, the dose will be reduced back to the corticosteroid stable dose for the remainder of the study, and visits will continue as per protocol. If the exacerbation occurs during Phase II, the dose of inhaled corticosteroid will be increased to the corticosteroid stable dose and maintained for the remainder of the study; no additional dosing tapers will be attempted. Additional treatment for exacerbations is at the treating physician's discretion (see Section 2 below).

1. Treatment Failure Rescue Algorithm

Home Care

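### The automatic toxicity notice does not name the Exit-visit 25(OH)D, so a toxic level found at exit has no stated route to the blinded site

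*Protocol*

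**What the plan says.** The Exit visit is described in VI.C under "Exit visit (in those participants who have been randomized and are withdrawing consent" or who meet drop-out criteria because of more than two treatment failures. X.G confirms that a participant with a third event "will be seen in the AsthmaNet clinic for a final study exit visit". The Exit list contains one laboratory test, serum 25(OH)D. It has no urine calcium/creatinine ratio and no serum calcium. Appendix E has no Exit column.

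On 25(OH)D, VI.D states: "Participants will have peripheral blood collected for vitamin D level at visits 0, 6, 8 and 10". Participants, clinic staff and the coordinating-centre staff who run the trial day to day "will not have access to the actual assay results from the screen visit or follow-up visits". The notification rule opens: "If a follow-up vitamin D level (from visit 6, 8, or 10) is in the toxic range". An e-mail then goes to the site without giving the value. The toxic threshold is 120 ng/ml. VI.D and IX.B require capsules to stop and the test to be repeated; if the repeat is also toxic, IX.B adds referral to primary care.

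On calcium, VI.D says of the urine ratio that "this is the earliest abnormality detected and most non-invasive way of monitoring for hypervitaminosis D", and both VI.D and IX.B say that the "ratios will be measured at visits 1, 3, 5, 6, 8 and 10". Serum calcium is scheduled only at Visit 1, and otherwise follows a repeated raised ratio.

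**The concern.** The protocol orders a safety-relevant blood test at exit but does not connect its result to the one mechanism that would tell a blinded site about a toxic value. The 120 ng/ml rule is not limited by visit, but a site cannot act on a result that it is not told. IX.A says that levels obtained during the study serve to monitor for toxicity, so the Exit draw is presumably meant to count.

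At stake is follow-up of a small group after treatment: a confirmatory repeat and, if confirmed, referral. A participant who has left has no later study visit at which the level would be picked up.

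**Working it through.** The plan gives no figure to reproduce here. The check sets the sections side by side and then sizes the group.

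**Trace of an Exit sample**

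1. Drawn? Yes, by the VI.C Exit list.
2. In the VI.D draw list? No. That list has visits 0, 6, 8 and 10.
3. Visible to site staff? No. VI.D blinds them to screening and follow-up values.
4. Covered by the automatic e-mail? Not as worded. It names visits 6, 8 and 10.
5. Subject to the 120 ng/ml rule? Yes, in VI.D and IX.B, but only if someone tells the site.

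Visit 10 is the useful comparison. It also ends treatment, and there the 25(OH)D is in the draw list and the alert, and the urine ratio is collected.

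**Timing**

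- Randomization and first blinded dose: Visit 4, week 5.
- First scheduled on-treatment urine ratio: Visit 5, week 11, so 11 − 5 = 6 weeks after randomization.
- First scheduled on-treatment 25(OH)D: Visit 6, week 17, so 17 − 5 = 12 weeks after randomization.

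Someone leaving before Visit 6 therefore has the Exit sample as their only scheduled 25(OH)D after the load. Someone leaving before Visit 5 also has no scheduled on-treatment calcium measure.

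**Size**

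Inputs: 200 per group and 15% withdrawal (VIII.A), and 28 weeks of treatment. Assumptions: the 15% covers all exits, every leaver attends and gives blood, exits are spread evenly over time, and they split equally between arms.

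- All exits: 400 × 0.15 = 60, or 30 on vitamin D.
- Before Visit 6: 60 × 12/28 = 25.7, or 12.9 on vitamin D.
- Before Visit 5: 60 × 6/28 = 12.9, or 6.4 on vitamin D.

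The protocol does not give the timing of exits. At half to double the even rate, the vitamin D numbers are 6.4 to 25.7 before Visit 6 and 3.2 to 12.9 before Visit 5.

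X.D expects "the bulk of treatment failures likely to occur during the inhaled corticosteroid tapering phase", and withdrawal for failure needs a third event, so the earliest exits should be mainly consent withdrawals.

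**How likely a toxic level is**

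Entry requires a level below 30 ng/ml. VII.B cites an average rise of 14.9 ng/mL after a single 100,000 IU dose; 30 + 14.9 = 44.9. It also cites a mean of 45 ng/ml on 4,000 IU/day, and it expects the trial regimen to give 40-100 ng/mL. The threshold of 120 is 20 ng/mL above the top of that range.

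**The case against.** The strongest reply is that the lists in VI.D are shorthand for numbered visits. They also leave the Exit visit out of the spirometry and Asthma Control Test schedules, although the Exit list has both. The protocol also calls for 25(OH)D draws outside visits 0, 6, 8 and 10, after a repeated raised urine ratio and after a toxic level, and it plainly expects those results to be acted on. On this view the parenthesis in the alert sentence is loose wording and the database may well flag any toxic value. This stands as far as the draw list goes: its omission of the Exit visit is editorial. It does not remove the alert gap, because that sentence is the only route stated and it names its visits.

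A second reply is that drug has stopped at exit, so nothing remains to be done. But Visit 10 also ends treatment and keeps the alert, and IX.B attaches a repeat test and a referral to a toxic level, not only stopping capsules.

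A reader might go further and infer that leaving the urine ratio off the Exit visit is an error. The documents do not support that. The VI.D and IX.B schedules, the Exit list and Appendix E agree that no ratio is planned at exit. Its hold, stop and resume steps are moot once drug has ended, and no participant at all has a ratio before Visit 5. Nor is a separate rule needed for repeating a raised ratio at a final visit, since the existing 30-day repeat in VI.D is not limited by visit.

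**Conclusion.** The alert gap holds on the text and is minor. Followed literally, the protocol leaves a toxic Exit 25(OH)D unreported to the site. On the planned withdrawal, about 60 Exit samples (about 30 on vitamin D) fall outside the alert. For about 26 of those participants (about 13 on vitamin D), the Exit sample is the only scheduled post-load level. These counts rest on a sample-size allowance and on assumed timing and attendance, so they give an order of magnitude only.

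A reader might infer that early leavers face a real toxicity hazard. The protocol's own figures point the other way: levels of 40-100 ng/mL are expected, the cited six-month dosing study found no toxicity, and the protocol itself expects the alert to be needed very seldom. The number of missed events may well be zero. The primary analysis is not affected.

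The absent urine ratio is a design choice that could be improved cheaply. It is not a contradiction.

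**What to change.** In VI.D, add the Exit visit to the 25(OH)D draw list, and change the parenthesis in the alert sentence to read: *from visit 6, 8, 10 or the Exit visit*. Check that the database e-mail is set to fire for Exit samples. This costs a few words in an amendment and one database check; the blood is already being drawn.

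Optionally, add a spot urine calcium/creatinine ratio to the Exit list in VI.C, for participants who agree, matching Visit 10. Its main use would be for those leaving before Visit 5, who otherwise have no scheduled on-treatment calcium measure. On the planned withdrawal, the cost is at most about 60 urine samples and a few repeats, and a 30-day repeat may be hard to obtain from people who are withdrawing. No threshold, dosing rule or analysis needs to change.
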